7.1. Study Patients

7.1.1. Disposition of Patients

Patient enrollment and disposition including number of patients screened, enrolled, dosed, and percentage of patients who discontinued from the study, along with reasons for discontinuations will be tabulated and described in listings.

7.1.2. **Protocol Deviations**

Analyses of protocol deviations will not be included in the CSR.

7.1.3. Demographics, Disease Characteristics and History

7.1.3.1. Demographics

Demographic and baseline characteristics will be summarized descriptively. Age at study entry (years), gender, race, ethnicity, baseline weight, baseline height and baseline Body Mass Index (BMI) will be summarized. Listings will also be provided.

7.1.3.2. Disease Characteristics

Disease characteristics will not be included in the CSR.

7.1.3.3. Medical / Surgical History and Baseline Physical Examination

Medical/surgical history and physical examination data will not be included in the CSR.

7.1.4. Prior and Concomitant Medications / Therapies

All medications and treatments received by the patient during the study or within the preceding 4 weeks will be collected. Any medication or treatment received after the first dose of SBC-103 will be considered concomitant. Medications will be mapped to a generic term using the current Alexion version of World Health Organization (WHO) Drug Dictionary (WHO-DD). Medications will be classified using the Anatomical Therapeutic Chemical (ATC) classification system. All prior and concomitant medications/therapies will be provided in listings.

7.2. Efficacy Analyses

7.2.1. Primary Analysis

As stated above, the primary objective of this study is to evaluate the safety and tolerability of IV administration of SBC-103, and as such, there is no primary efficacy endpoint or analysis.

7.2.1.1. Handling of Dropouts or Missing Data

Partial dates will be handled as detailed in Appendix 9.4.3 including details for calculating calendar or chronological age, as necessary. Missing data will be handled as detailed below for each measure.

7.2.1.2. Subgroup Analysis

Not applicable.

7.2.1.3. Multicenter Studies

Only 1 center participated in this study and therefore, analyses by center will not be performed.

7.2.1.4. Hypothesis Testing and Significance Level

Data analysis and/or presentation for this study are primarily descriptive in nature; therefore, no inferential analyses are planned and p-values will not be provided.

7.2.1.5. Sensitivity Analyses

Not applicable.

7.2.2. Secondary Analyses

Analyses of secondary efficacy endpoints will not be included in the CSR.

7.2.2.1. Neurocognitive and Developmental Assessments

Analyses of neurocognitive and developmental assessments will not be included in the CSR.

7.2.2.2. MRI Findings

Analyses of MRI findings will not be included in the CSR.

7.2.2.3. Blood Brain Barrier (BBB) Integrity Assessments

CSF/serum albumin index (CSF-AI) assessments of BBB integrity will be provided in listings.

7.2.2.4. Pharmacokinetic and Pharmacodynamic Analyses

7.2.2.4.1. Pharmacokinetic Analyses

Analyses of pharmacokinetic (PK) data will not be included in the CSR.

7.2.2.4.2. Pharmacodynamic Analyses

Analyses of pharmacodynamic (PD) data will not be included in the CSR.

7.2.3. Tertiary Analyses

Not applicable.

7.2.4. Other Efficacy Analyses

Not applicable.

7.2.5. Exploratory Analyses

No exploratory analyses will be included in the CSR.

7.3. Safety Analyses

As stated above in Section 5.2, the primary objective of this study is the safety and tolerability of SBC-103 in subjects with MPS IIIB. Descriptive statistics will be computed for specified safety parameters using the Safety Analysis Set, as appropriate, including treatment emergent adverse events (TEAEs), treatment emergent serious adverse events (TESAEs), and infusion-associated reactions (IARs) which are adverse events of special interest (AESI). The incidence of anti-drug antibodies (ADA) including ADA titer by time point, peak ADA titer, ADA titer status (positive/negative), neutralizing antibodies, and the relationship between ADA-positivity and the incidence of IARs will be presented.

7.3.1. Study Duration, Treatment Compliance, and Exposure

Dosing administration information will be listed by patient number and visit and will present details on confirmation of SBC-103 administration, reasons SBC-103 was not administered, total # of vials used, target dose (mg/kg), and dose concentration (mg/mL). Exposure to study drug (SBC-103) related information will be listed by patient number and visit. The stop/start dates/times, total actual volume of drug infused (mL), infusion rate (mL/hr), type of infusion (dosing or saline flush), rate reduction percentage compared to previous infusion rate, and information on any modification to the infusion including reason for modification will be presented in the listings.

7.3.2. Adverse Events (AEs)

Information will be summarized on all AEs that began at any time from the date of first study procedure performed through the last procedure at the last study visit. Adverse events will be

classified by the study Investigator into one of the following relations to study drug: not related, unlikely related, possibly related or related to study drug. For reporting purposes, "related" events will include all AEs assessed by the Investigator as: possibly related or related to study drug.

All AEs captured in the eCRF will be coded using the Medical Dictionary for Regulatory Activities (MedDRA) coding system and displayed in tables and data listings using System Organ Class (SOC) and Preferred Term (PT). All AEs will be coded using the MedDRA, version 13.1 or higher.

Severity of AEs will be graded on a 3-point scale (mild, moderate and severe) based on the definitions, developed from Clinical Data Interchange Standards Consortium (CDISC) Study Data Tabulation Model (SDTM) standard terminology v3.1.1 (see Protocol Section 7.1.1).

Adverse event incidence will be reported based on the concept of treatment emergence for the purposes of this analysis. Any AE that occurs after the first dose of SBC-103 is considered a treatment emergent adverse event (TEAE) for this study.

Adverse events are summarized by patient incidence rates; therefore, in any tabulation, a patient contributes only once to the count for a given AE.

The number and percentage of patients with a TEAE will be summarized.

7.3.2.1. Overall Summary of Adverse Events

An overall summary of TEAEs and treatment-emergent SAEs (TESAEs) will include summaries of events (n) and number of patients with events (n, %).

Within each summary category (TEAEs, TESAEs) the following subcategories will also be summarized, as appropriate:

- At Least 1 TEAE
- At Least 1 Severe TEAE
- At Least 1 Related TEAE (possibly related or related to study drug)
- At Least 1 TEAE Leading to Withdrawal / Discontinuation from the Study
- At Least 1 IAR
- At Least 1 Serious TEAE

Additionally, the number and percentage of patients who died on study will be presented.

7.3.2.2. AEs and SAEs by System Organ Class (SOC) and Preferred Term (PT)

The number of TEAEs and the number and percentage of patients with events will be descriptively summarized and presented by SOC and PT. Patients are counted once in each SOC and PT. Percentages will be based on the total number of treated patients.

The number of Serious TEAEs and the number and percentage of patients with events will be descriptively summarized and presented by PT. Patients are counted once in each PT. Percentages will be based on the total number of treated patients.

All AEs will be presented in by-patient listings.

7.3.2.3. AEs and SAEs by SOC, PT, and Relationship

Individual patient AE/SAE data for Relationship to Study Drug and Relationship to Study Procedures is presented in the by-patient AE listings.

7.3.2.4. AEs and SAEs by SOC, PT, and Severity

Individual patient AE/SAE data for severity is presented by-patient AE listings.

7.3.2.5. Deaths, Other SAEs, and Other Significant Adverse Events

Deaths and other SAEs will be identified by the data presented in the by-patient listings of AEs.

7.3.2.5.1 Other Significant Adverse Events

Procedure-related AEs will be identified by the relationship to study procedures data presented in the by-patient listings of AEs.

7.3.2.5.2. Infusion-Associated Reactions

Infusion-associated reactions (IARs) will be considered AEs of special interest (AESIs). An AE will be considered an IAR if it meets either of the following criteria:

- The Investigator checks "Yes" to the question "Is AE an IAR?" on the AE eCRF.
- The AE (diagnosis and/or symptom) occurs between the start of the infusion up to 4 hours after the infusion and is assessed by the Investigator as at least possibly related to Investigational Medicinal Product (IMP).

Note that several AEs may be associated with 1 IAR observed with SBC-103 administration; each AE is captured as a separate event. The number and percentage of patients who experience any IAR and the number of IARs reported over the course of the study will be summarized. Any patient who experiences an IAR is only counted once regardless of the number of associated events. Patients may be counted more than once if IARs occur on more than 1 dosing day.

Summaries of AEs that comprise an IAR will be displayed by MedDRA PT. Each patient will be counted only once within each PT.

A by-patient data listing of all AEs will be presented.

7.3.3. Other Safety

7.3.3.1. Analyses for Laboratory Tests

The clinical laboratory data to be presented include hematology, chemistry, urinalysis, coagulation, renal function, liver function, CSF findings and CSF-AI ratio. All clinical laboratory data will be listed.

Clinical laboratory values by time of assessment will be expressed in International System of units (SI units) in data listings. Unscheduled lab test results will also be presented in the data listings. Abnormal lab values will be flagged with "H"/"L" or "HIGH"/"LOW" for out of range values, and an asterisk for clinical significance in the data listings.

Patient data for clinical laboratory data will be presented in listings by patient number and visit.

7.3.3.2. Vital Signs

Vital signs include systolic blood pressure, diastolic blood pressure, heart rate, respiratory rate, and body temperature. A listing of vital signs will be presented by patient number, vital sign parameter, vital sign value, and visit.

7.3.3.3. Other Safety Parameters of Special Interest

7.3.3.3.1. Antidrug Antibody (ADA)

Assays testing for screening, confirmed, neutralizing ADA will be performed and ADA titers will be measured for neutralizing antibodies. For this analysis, confirmed ADA assay results will be descriptively presented by ADA status (Positive, Negative) as the proportion of patients, n (%), with measurable confirmed antibodies to SBC-103 for each visit. Neutralizing antibodies for confirmed positive cases will also be presented.

ADA titer result statistics will be descriptively presented by ADA status and visit.

The number and percentage of patients with Infusion-Association Reactions (IARs) adverse events by MedDRA System Organ Class, Preferred Term, and ADA positivity will be presented along with the number of IAR events. If a patient experienced more than one event in a given SOC, that patient is counted once for that SOC. If a patient experienced more than one event with a given PT, that patient is counted only once for that PT.

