The potential toxicity of SBC-103 was evaluated in Cynomolgus monkeys following repeated IV doses of SBC-103 (1, 3, 10 or 20 mg/kg qw) for 4 weeks with a 2-week recovery period (SBC103-T008). There were no changes in clinical observations, macroscopic, organ weight or microscopic findings that were considered SBC-103-related. The incidence of anti-SBC-103 IgG antibodies in samples collected at study termination was approximately 80% in SBC-103 treated animals (irrespective of the dose). No anti-SBC-103 antibody formation was detected in any control animals. The administration of SBC-103 at these IV dose levels was well tolerated. Consequently, the NOAELs in this study were considered to be 10 mg/kg/dose qw and 20 mg/kg/dose qow.

The potential toxicity of SBC-103 was evaluated in juvenile Cynomolgus monkeys following repeated qw IV doses of 3 and 10 mg/kg or qow at 20 mg/kg during a 3-month dosing period with a 4-week recovery period (SBC103-T009). There were no SBC-103-related mortalities and no macroscopic, organ weight, or microscopic changes that were considered SBC-103-related. Transient clinical signs were noted but there were no correlating findings in any of the other parameters evaluated. The transient clinical signs included, but were not limited to, decreased activity, hunched posture, lying on side, abnormal gait, uncoordination, excessive scratching/cage manipulation and/or repetitive behaviour. The presence of anti-SBC-103 IgG antibodies was confirmed in 87%, 60% and 87% animals from 3 mg/kg, 10 mg/kg, and 20 mg/kg dose respectively and no animals in the control group were confirmed positive for anti-SBC-103 antibody. Antibody titres did not increase with dose level administered. Consequently, the NOAELs were considered to be 10 mg/kg/dose (qw) and 20 mg/kg/dose (qow) in this study.

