3.4 Study Endpoints

3.4.1 Primary Endpoint

The primary endpoint of this study is safety and tolerability of SBC-103 in subjects with MPS IIIB. The safety assessments will include the following:

- Incidence of AEs, SAEs, and IARs.
- Changes from baseline in clinical laboratory tests (haematology, serum chemistry, and urinalysis) and CSF findings (cell counts, glucose, and protein).
- Changes from baseline in 12-lead ECGs.
- Changes in vital signs during and post-infusion, relative to pre-infusion values.
- Physical examination findings.
- Use of concomitant medications/therapies.

• Incidence of ADAs, including seroconversion rate, time to seroconversion, and ADA titre by time point, peak ADA titre, and ADA titre status (positive/negative), and the effect of ADAs on the safety of SBC-103, including the relationship between ADA-positive subjects and the incidence of IARs.

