5.2. Safety

The primary endpoint of this study is the safety and tolerability of SBC-103 in subjects with MPS IIIB. The safety assessments will include the following:

- Incidence of treatment emergent adverse events (TEAEs), treatment emergent serious adverse events (TESAEs), and infusion-associated reactions (IARs) which are adverse events of special interest (AESI).
- Incidence of anti-drug antibodies (ADA) including ADA titer by time point, peak ADA titer, and ADA titer status (positive/negative), and the effect of ADAs on the safety of SBC-103, including the relationship between ADA-positive subjects and the incidence of IARs.

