9.3. Sample Size, Power, and Randomization

9.3.1. Sample Size and Power

The sample size of up to 5 subjects was determined by the number of subjects enrolled in the prior NGLU-CL01 study, based on clinical and not statistical considerations and is considered sufficient to provide PK, safety, and PD/efficacy data, which in combination with data from other NGLU studies could be used to inform dose selection, regimen, and study design for future studies.

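### The IAR table is split by an ADA positivity that is neither defined nor ordered in time, so it cannot show whether reactions followed antibody development

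*SAP*

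**What the plan says.** Protocol 3.4.1 makes the effect of ADA on safety part of the primary endpoint, "including the relationship between ADA-positive subjects and the incidence of IARs". SAP 5.2 keeps this as "the relationship between ADA-positive subjects and the incidence of IARs". SAP 7.3 says that "the relationship between ADA-positivity and the incidence of IARs will be presented".

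The only table that does this is in SAP 7.3.3.3.1. It gives the number and percentage of patients with IARs by System Organ Class, "Preferred Term, and ADA positivity will be presented along with the number of IAR events", and counts each patient once per class and once per term. ADA positivity is not defined for this table, and no denominators by ADA group are given. The same section tabulates the proportion of patients "with measurable confirmed antibodies to SBC-103 for each visit", but that table is not crossed with IARs.

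The protocol endpoint also covers "Incidence of ADAs, including seroconversion rate, time to seroconversion, and ADA titre by time point". The SAP 5.2 list keeps titre by time point but has neither seroconversion rate nor time to seroconversion.

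**The concern.** ADA status can change during treatment, and the clinical question is one of sequence: did reactions follow the antibodies? A table with one undefined status per patient does not answer it. Someone programming from the SAP could choose ever-positive, baseline or at-event status, and the same data would then give different tables.

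The wording about ADA-positive subjects, with patients as the counting unit, makes one status per subject the natural reading. Reactions before the first positive sample would then appear under ADA-positive. In a study this small, the comparison group could also disappear.

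No other planned summary restores the order. Time to seroconversion is not in the SAP list. SAP 7 displays summaries under the 3 mg/kg dose regardless of the initial 1 mg/kg period, so dose period does not separate early events from late ones.

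**Working it through.** The plan states no figure for this analysis, so there is nothing to reproduce. The checks below use the schedule of assessments and the sample size ("The sample size of up to 5 subjects was determined by the number of subjects enrolled in the" earlier study).

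**1. Schedule**
- Planned infusions, Weeks 0, 2, …, 156: 156/2 + 1 = 79.
- Scheduled pre-dose ADA samples, Day 0 then every 4 weeks to Week 156: 156/4 + 1 = 40.
- Planned infusions without a scheduled same-day ADA sample: 79 − 40 = 39. Each of these has a scheduled sample at the dosing visit before it.
- The first scheduled on-treatment sample is at Week 4. If the first positive sample is at Week w, the number of planned infusions before it is w/2: 2 for Week 4, 4 for Week 8, 6 for Week 12 and 12 for Week 24.

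These are full-plan counts. SAP 4 records that the program was stopped on 11 July 2017, so actual counts may be lower.

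**2. What the missing definition changes**

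Take a hypothetical child with IARs at Weeks 2, 6 and 20 who is negative at Day 0, first positive at Week 12 and positive thereafter.

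| Meaning of ADA positivity | IARs under ADA-positive | IARs under ADA-negative |
|---|---|---|
| Ever positive | 3 | 0 |
| Status at Day 0 | 0 | 3 |
| Latest result at or before the infusion | 1 | 2 |

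All three fit the SAP wording, and only the last reflects sequence.

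**3. Chance of an empty ADA-negative group**

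For an assumed ever-positive rate p and 5 independent subjects, P(no negative subject) = p⁵ and P(at most one negative) = p⁵ + 5p⁴(1 − p).

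| p | No negative subject | At most one |
|---|---|---|
| 30% | 0.002 | 0.031 |
| 50% | 0.031 | 0.188 |
| 60% | 0.078 | 0.337 |
| 80% | 0.328 | 0.737 |
| 87% | 0.498 | 0.871 |
| 100% | 1 | 1 |

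The documents give no human rate. The values from 60% up are animal figures in Protocol 1.3: 60% and 87% in juvenile monkeys, 100% in rats, and in the 4-week monkey study the incidence "was approximately 80% in SBC-103 treated animals (irrespective of the dose"). The same section says that nonclinical studies do not predict human immunogenicity. The table is therefore a range of assumptions, not a forecast.

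**4. Direction of distortion under an ever-positive rule**

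Assume all subjects receive 79 infusions, with IAR risk r per infusion before positivity and Rr after it, and k infusions before the first positive sample. Expected IARs are r[k + R(79 − k)] in an ever-positive subject and 79r in a never-positive one. The ratio is [k + R(79 − k)]/79.
- R = 1: ratio 1 for any k.
- R = 2: (2 + 154)/79 = 1.97 for k = 2; (12 + 134)/79 = 1.85 for k = 12.
- R = 4: (2 + 308)/79 = 3.92 for k = 2; (12 + 268)/79 = 3.54 for k = 12.

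With equal follow-up, the misallocation creates no link where none exists and slightly dilutes a real one. Unequal follow-up, or the extra ADA sample after a moderate or severe IAR (footnote 6 of the schedule), could act differently.

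**The case against.** The strongest reply is that the order can be recovered. There are at most 5 subjects. SAP 7.3.2.2 puts all AEs in by-patient listings, SAP 7 adds the relative study day to dated listings, SAP 7.3.1 lists dosing by patient and visit, and SAP 5.2.3 puts laboratory results, naming ADA testing, in listings. The analysis is descriptive with no p-values, and a subject-level table follows the protocol's own endpoint wording. All of this stands and limits the harm. It does not make the planned table interpretable, and it leaves the sequence for each reader to rebuild by hand.

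A reader might infer that the SAP prescribes an ever-positive rule. It does not: positivity is undefined, and the only status described in SAP 7.3.3.3.1 is per visit. Subject-level status is the natural reading, not a stated one.

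A reader might also infer that the table is biased towards an ADA–IAR link. The documents do not support that, and step 4 shows slight dilution when follow-up is equal.

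Nor would the table be worthless if every subject became positive. It would still report IAR incidence in ADA-positive subjects. The missing comparator would come largely from the sample size.

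**Conclusion.** The point holds as a gap in definition and time ordering. On the subject-level reading, IARs at up to 2, 4, 6 or 12 planned infusions per subject would be counted under ADA-positive before a positive result at Week 4, 8, 12 or 24. The chance of no ADA-negative subject runs from 0.2% at an assumed 30% rate to 50% at 87%, and is certain at 100%. These figures rest on the full planned schedule, 5 treated and independent subjects, and assumed positivity rates.

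The direction of any distortion is not established. The change should be made because the ADA–IAR relationship is part of the primary endpoint and the correction is cheap. The listings keep it from being a critical defect.

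**What to change.** In SAP 7.3.3.3.1:

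- Keep the subject-level table. Define ADA positivity for it, for example as any confirmed positive post-baseline sample, and state the denominator in each group.
- Add a time-aligned summary. Each infusion takes the latest confirmed pre-dose ADA result at or before it, carried forward where there is no same-day sample. Each IAR takes the status of its infusion. An IAR designated by the investigator outside the 4-hour window takes the status of the most recent infusion.
- Report IARs per infusion, and subjects with an IAR, by that status. Show the dose at the infusion and present subjects positive at Day 0 separately.
- Add a per-subject display of IAR dates against ADA status, titre and dose.

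The cost is SAP wording, one derived variable and two outputs. Pre-dose ADA samples, infusion times and the times of AEs within 24 hours of infusion are already collected.

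Two limits should be stated with the output. A subject can appear in both status columns. ADA status within a subject is also confounded with dose and time on treatment: SAP 7 says that all subjects received 1 mg/kg for the first 12 weeks and were then escalated to 3 mg/kg. For a subject first positive at Week 12 who stays positive, all 6 earlier planned infusions fall in the 1 mg/kg period. The summary shows sequence and does not estimate an ADA effect.

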7.3.3.3.2. ECG

Analyses of ECG data will not be included in the CSR.

8. **REFERENCES**

Statistical Analysis Plan {01 Sep 2017, Version 1.0}

9. **APPENDICES**

